calculated for the primary endpoint of time to death or hospital re-admission within the 6 month post-discharge period, assuming an alpha level of 0.05, power of 0.80, and a ratio of treatment to placebo random assignment of 1:1. In sub-Saharan Africa, it is estimated that 2-15% of children aged less than 5 years died within 6 months of hospital discharge 15.5% of children who survived discharge from the district hospital re-admitted with the same diagnosis within 6-months[7, 9, 25] Assuming

an additional 5-10% of children are re-admitted for other conditions, we expect that re-hospitalizations will occur in 20.5 to 30.5% of children enrolled in the study. Combined with our expected fatality rate (2-15%), we expect the cumulative incidence of the combined endpoint to range from 22.5 to 45.5%. [25] Based on a previous trial of mass drug administration of a single dose of azithromycin in which a single dose of the antibiotic was associated with a 49% reduction in risk of death, we calculated sample sizes using estimates of reduction in risk ranging from 30-50% with the cumulative incidence range of 22.5 to 45.5%, and found the sample size required ranged from 90 to 550 children per treatment arm.[10] Using the most conservative estimates of a hazard ratio of 0.70 and 22.5% prevalence of re-admission/death, we need to enroll 1100 children in the study (550 per arm) to achieve adequate power. We will recruit an additional 300 children ($\approx 20\%$) to account for possible loss to follow-up, resulting in a total planned enrollment of 1400 children, or 700 per treatment group. When considering mortality alone, and estimated mortality ranges of 2-15%, we will have $>80\%$ power to detect hazard ratios ≤ 0.5 for mortality rates of $\geq 8\%$ and hazard ratios ≤ 0.6 for mortality rates $\geq 11\%$ (Figure 6). Although the ability to determine differences in mortality between arms will require either a high mortality rate or a large measure of effect, in Kenya, re-hospitalization is associated with as much as a 23.6-fold increased risk of death, indicating that this outcome is itself a severe outcome and an intermediate marker of death.[7]

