**Azithromycin to prevent post-discharge morbidity
and mortality in Kenyan children**

Toto Bora Trial

NCT02414399

Statistical Analysis Plan Version 5.0 (May 29, 2020)

TABLE OF CONTENTS

SECTION 1. ADMINISTRATIVE INFORMATION	2
Title	2
Trial Registration	2
SAP Version	2
Protocol Version	2
SAP Revision History	2
SECTION 2. INTRODUCTION	3
Background and Rationale	3
Objectives.....	3
SECTION 3. STUDY METHODS	4
Trial Design	4
Randomization	4
Sample size	4
Framework.....	4
Statistical Interim Analysis and Stopping Guidance.....	5
Timing of Final Analysis	5
SECTION 4. STATISTICAL PRINCIPLES	6
Confidence Intervals and P values	6
Analysis Populations	7
SECTION 5. TRIAL POPULATION	7
Screening Data.....	7
Eligibility	7
Recruitment.....	7
Baseline Patient Characteristics	8
SECTION 6. ANALYSIS	10
Outcome Definitions.....	10
Analysis Methods	11
Missing Data.....	15
Harms.....	15
Statistical software	16
References	16

SECTION 1. ADMINISTRATIVE INFORMATION

Title: Statistical Analysis Plan for Azithromycin to prevent post-discharge morbidity and mortality in Kenyan children: a protocol for a randomized, double-blind, placebo-controlled trial (the Toto Bora trial).

Trial Registration: NCT02414399

SAP Version: 5.0 (29May2020)

Protocol Version: 12Dec2017

SAP Revision History

SAP Revision history Version (date)	Justification for each SAP revision	Timing of SAP in relation to interim analysisⁱ
1.0 (21-Nov-2015)	Original	Before
2.0 (15-Mar-2016)	The DSMC reviewed our SAP and made suggestions which were implemented in an updated version. These changes included: plans for checking proportional hazards assumption, explicit mentioning of informative censoring, and addressing missing data. Specified interim analysis stopping rules and alpha boundary for final analysis. Added statistical analysis plan of secondary aims.	Before
3.0 (24 Aug 2017)	Clarified the primary outcome definition to exclude re-hospitalizations that were a continuation of the management prescribed as part of the original hospitalization or that occur during enrollment procedures (therefore hospitalizations that likely started prior to the investigational product being administered). Added the definition of loss to follow-up and a shell-table demonstrating how this information would be reported in quarterly reports. Updated the shell table for how adverse events would be reported by categories AE's in terms of Grade as opposed to specific AE's.	Before

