A single interim analysis for re-hospitalization-free survival will be performed using O'Brien-Fleming boundaries for benefit or harm when 50% of expected person time (350 child-years) has been accrued. Assuming 157 events will be available at half of the person-time accrual, a z-score critical value of 2.797, or p -value < 0.005 , from a Kaplan Meier log-rank test will determine the cut-off of statistical significance. A symmetric boundary will be used for benefit or harm. The DSMC will review this analysis and make a determination about continuing the study. Futility will not be a basis for stopping rules because of the trials' value in understanding mechanisms of post-discharge worsening and antibiotic resistance. Assuming the DSMC decides to continue the trial after the interim analysis, an alpha of 0.045 will be used as the statistical significance boundary at the final analysis for the primary hypothesis test.

Timing of Final Analysis

The first main report/ publication of the trial will be prepared for the primary aim when every enrolled child has completed their 6 month follow-up visit or is deemed lost to follow-up and all primary endpoint data has been cleaned (anticipated publication in September 2020).

Timing of Outcome Assessments

The schedule of study procedures is outlined in Table 1. Regularly scheduled visits include those at M0 (hospital discharge), M3, and M6. Participants are actively followed for 1 month following their missed visit. If a visit occurs after the one month window, relevant data will be ascertained when possible, but may not be included in the analysis (as described in Table 1). The start date/time for each participant is the date/time of randomization.

Table 1. Allowable windows for each outcome

Outcome	Visit Window
Death or re-hospitalization	Follow-up time censored 180 days after enrollment or at the time of the last follow-up visit (if < 180 days). Data collected (including vital status) from visits that occur beyond 180 days will be included but events and person-time will be censored at 180 days.
Cause specific hospitalization	Follow-up time censored 180 days after enrollment or at the time of the last follow-up visit (if < 180 days). Data collected (including vital status) from visits that occur beyond 180 days will be included but events and person-time will be censored at 180 days

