Prevalence of Shigella , Salmonella , Campylobacter , Cryptosporidium , Giardia @ enrollment, day 90, and day 180	Visits that occur within 30-days on either side of 90-days (M3) and 180-days (M6) visits will be included. Therefore, visits occurring outside of 60-120 days post-enrollment for M3 and outside of 150-210 days post enrollment for M6 will be excluded from the primary analysis but included in sensitivity analyses.
Streptococcus pneumoniae (S. pneumoniae) prevalence @ enrollment, day 90, and day 180	Visits that occur within 30-days on either side of 90-days (M3) and 180-days (M6) visits will be included. Therefore, visits occurring outside of 60-120 days post-enrollment for M3 and outside of 150-210 days post enrollment for M6 will be excluded from the primary analysis but included in sensitivity analyses.
Prevalence of resistance to azithromycin in E.coli and S. pneumoniae and prevalence of ESBL-producing E.coli @ enrollment, day 90, and day 180	Visits that occur within 30-days on either side of 90-days (M3) and 180-days (M6) visits will be included. Therefore, visits occurring outside of 60-120 days post-enrollment for M3 and outside of 150-210 days post enrollment for M6 will be excluded from the primary analysis but included in sensitivity analyses.

SECTION 4. STATISTICAL PRINCIPLES

Confidence Intervals and P values

Level of statistical significance

All statistical tests will be 2-sided using a 5% significance level (alpha of 0.05). For the primary aim (aim 1), an alpha of 0.045 will be used for hypothesis tests that were part of the interim analysis to account for alpha spending.

Type I errors

We will not adjust the alpha for multiple testing in the primary aim. Instead we will clearly state primary and secondary analyses and interpret secondary analyses as hypothesis-generating rather than confirmatory. All secondary aims will be adjusted for multiple comparisons using the Benjamini and Hochberg method using a false discovery proportion of 0.05.

Confidence intervals to be reported

For the primary analysis of Aim 1, two-sided 95.5% confidence intervals will be used to account for the 0.045 alpha spent at the interim analysis. All other analyses will utilize two-sided 95% confidence intervals.

Adherence and Protocol Deviations

Definition of adherence to intervention and how this is assessed including extent of exposure

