Prescribed antibiotics at discharge			
Nutritional, HIV, and Vaccine Status			
Breastfeeding status (in first 6 months of life)			
Exclusively breastfed			
Partially breastfed			
Never Breastfed			
Unknown			
Stunted (HAZ < -2)			

Underweight (WAZ < -2)			
Acute Malnutrition			
Severe (WHZ < -3 or MUAC <11.5cm or edema)			
Moderate (-3 ≥ WHZ < -2 or 11.5 ≥ MUAC <12.5cm)			
HIV-status			
HIV- infected			
HIV-exposed, uninfected			
HIV-exposed, unknown infection status			
HIV status unknown			
Received all age-appropriate vaccines			

SECTION 6. ANALYSIS

Outcome Definitions

Primary study end-points:

1. **Deaths** will be ascertained by study staff either through community health workers, hospital staff, or determined at follow-up visits. Date of death will be ascertained from the following (in order of prioritization): death certificate, hospital record, caregiver report
2. **Re-hospitalization** will be assessed by questionnaire at day 90 and 180 follow-up visits and medical record review. In cases when both sources are available, information from the medical record will be considered the gold standard. A hospitalization will be defined as an overnight stay, including situations where a child is admitted in the middle of the night (even if after midnight) and discharged the subsequent morning. Re-hospitalizations that are a continuation of management from the previous hospitalization (such as elective blood transfusion) or that occur during enrollment procedures, due to a clinical deterioration post-discharge, will be excluded from the analysis. To operationalize these exclusions, we will exclude re-hospitalizations that occur <2 hours after administration of the study medication and those re-hospitalizations that occur as a result of the child being advised to seek further care for a blood transfusion due to a lack of blood availability at the enrollment facility.
3. **Loss to follow-up** will be defined as non-attendance at both follow-up visits despite up to one month of active tracing and no clear evidence of death.
4. **Death or re-hospitalization** (combined) is the primary endpoint.

Secondary end-points:

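### The operational test for the continuation-of-management exclusion is narrower than the definition it implements, so applied literally other readmissions scheduled at discharge would count as primary events

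*SAP*

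**What the plan says.** SAP Section 6, Outcome Definitions, item 2, first sets out two excluded classes. One is "Re-hospitalizations that are a continuation of management from the previous hospitalization (such as elective blood transfusion"), where transfusion is offered as an example of a wider class. The other is readmission during enrollment procedures because the child deteriorated.

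The next sentence says how these exclusions will be applied and gives two tests. The first catches a readmission that starts within 2 hours of dosing. The second catches "those re-hospitalizations that occur as a result of the child being advised to seek further care for a blood transfusion due to a lack" (the enrollment facility having no blood). The 2-hour test serves the deterioration class. The blood-availability test is the only one for the continuation class.

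The SAP Revision History entry for version 3.0 describes the change in the wide sense, as excluding "re-hospitalizations that were a continuation of the management prescribed as part of the original hospitalization". Item 2 also defines a hospitalization as an overnight stay and makes no distinction between planned and unplanned stays. Under Analysis Methods, the primary model is a Cox regression of death or first re-hospitalization.

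**The concern.** The two sentences describe different sets of primary events. By the definition, a child booked at discharge for a planned overnight procedure, or to return and complete prescribed inpatient treatment, has no event. By the operational test, that child does. The test does not even cover the definition's own example in full: an elective transfusion that was deferred although the enrollment facility had blood meets the definition but not the test.

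A readmission already arranged at discharge cannot be prevented by a drug started at discharge. If it counts, it adds an event on which no effect is possible. In a first-event analysis it also closes the child's follow-up, so a later unplanned readmission or death is not seen. At stake are some attenuation of the primary hazard ratio, some power, and whether two analysts working from the same text would build the same primary dataset.

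**Working it through.** **Does any other text close the gap?**

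- The 2-hour test cannot reach a return booked for days or weeks later.
- SAP Section 5, Eligibility, leaves out children being referred to another facility and admissions for trauma, injury, poisoning or a birth defect. That removes some candidates, but not planned returns.
- Review by clinical consensus is specified for cause of death only (Outcome Definitions, item 5). No classification of readmissions as planned or unplanned is described, and no sensitivity analysis on the point.

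**Inputs for the size**

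- Design assumptions, Protocol Sample Size, Aim 1: "assuming an alpha level of 0.05, power of 0.80, and a ratio of treatment to placebo random assignment of 1:1", with "a hazard ratio of 0.70 and 22.5% prevalence of re-admission/death, we need to enroll 1100 children".
- Sidedness, SAP Section 4: "All statistical tests will be 2-sided using a 5% significance level (alpha of 0.05").
- Share q of placebo-arm primary events that are scheduled continuation admissions not caught by the present tests: not in the documents. Assumed values are 1%, 2%, 5% and 10%, with a hazard ratio of 1 for these admissions.

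**The plan's own figure.** Events needed = 4 × (1.960 + 0.842)² / (ln 0.70)² = 247. Children = 247 / 0.225 = 1098, which reproduces the stated 1100. Conversely, 1100 × 0.225 = 247.5, or about 248 events, and at that count power for a hazard ratio of 0.70 is 80%.

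**Dilution.** Composite HR = (1 − q) × 0.70 + q × 1 = 0.70 + 0.30q. Power = Φ(|ln HR| × √D / 2 − 1.96), with D = 248.

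Worked case, q = 5%: HR = 0.70 + 0.015 = 0.715; |ln 0.715| = 0.3355; 0.3355 × 15.75 / 2 − 1.96 = 0.68; Φ(0.68) = 75%.

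**Removal.** Scheduled events removed = D × 2q / (1 + HR). At q = 5% this is 248 × 0.10 / 1.715 = 14.5, leaving about 234 events at HR 0.70, with power 78%.

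| Assumed q | HR if counted | Power if counted | Events left if removed | Power if removed (HR 0.70) |
|---|---|---|---|---|
| 0% | 0.700 | 80% | 248 | 80% |
| 1% | 0.703 | 79% | 245 | 80% |
| 2% | 0.706 | 78% | 242 | 79% |
| 5% | 0.715 | 75% | 234 | 78% |
| 10% | 0.730 | 70% | 219 | 75% |

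The last column gives no credit for later unplanned events in children who stay at risk, so it is slightly pessimistic.

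**Sensitivity of these figures**

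- If the scheduled admissions come on top of the 22.5% instead of within it, power is 77% at q = 5% and 74% at q = 10%.
- SAP Section 3 states that "an alpha of 0.045 will be used as the statistical significance boundary at the final analysis". At that level, undiluted power with 247 events is 79%.
- If nobody is lost, 1400 × 0.225 = 315 events. Power is then 89% undiluted, about 85% at q = 5% and 80% at q = 10%.

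**The case against.** The strongest reply is that the governing sentence says continuation admissions are excluded, and the SAP nowhere says that non-transfusion ones count. The two tests might only illustrate the exclusion. That is a possible reading. But the tests are introduced as the way the exclusions are put into practice, so an analyst who programs the endpoint would naturally use them and nothing more. The ambiguity is itself the defect.

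A reader might go further and infer that planned admissions are in fact being counted and are diluting the result. The documents do not support that: they do not show that a single such admission occurred or was expected. Nor do they support an inference of bias toward one arm. The need is set at discharge, randomization balances it, and the type I error is unaffected. A reader might also extend the point to a child transferred between hospitals during one readmission. That could matter only for the secondary Andersen-Gill analysis of repeated hospitalizations; it cannot change a first-event analysis.

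Two further replies have some force. The protocol's primary outcome is mortality or readmission with no exclusions, so keeping these admissions is conservative and consistent with it. And 248 events is the less favorable count. The protocol recruits 300 more children "to account for possible loss to follow-up, resulting in a total planned enrollment of 1400 children", and if fewer are lost than allowed for, power is higher throughout. Both replies limit the size of the problem; neither reconciles the two sentences.

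Finally, the present tests are concrete, whereas a wider rule needs judgement, and some readmissions will be known only from the caregiver's questionnaire. That is why the fix needs a default for undocumented cases.

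**Conclusion.** The point holds as a mismatch between a definition and the test that implements it. By the SAP's own definition, the literal rule would misclassify any overnight readmission scheduled at the original discharge for a reason other than lack of blood. The consequence would be attenuation toward 1 and some loss of power, not bias toward an arm.

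The size rests wholly on an assumed share and on a hazard ratio of exactly 1 for these admissions. At 1% to 2% of placebo-arm events it is negligible (HR 0.703 to 0.706, a loss of 1 to 2 percentage points of power). At 5% it costs about 5 points and at 10% about 10, of which removal recovers about 3 and 5. The case for acting does not depend on a large share: the primary endpoint should be reproducible from its text, and at present it is not.

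**What to change.** Keep the two existing tests and add a third to Outcome Definitions, item 2: a readmission is excluded when the enrollment hospital record or discharge plan documents that it was scheduled or prescribed at the original discharge. Classify readmissions blinded to arm, before unblinding. Where no such documentation exists, including readmissions known only from the questionnaire, count the readmission as an event. Report the primary analysis under this rule, with a sensitivity analysis that uses only the two current tests.

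The cost is a short SAP amendment and one blinded pass over records. The protocol already has staff abstract the enrollment stay (Enrollment) and each readmission (Follow-up Procedures). The Enrollment list does not name a discharge plan, so some files may have to be reopened. A few events would be lost, and each record would need a small judgement, which the documentation requirement and the default keep narrow.

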Outcome	Azithromycin-treated group (N=)			Placebo-treated group (N=)			Effect Estimate		
	n	Person-time	Incidence rate (/100)	n	Person-time	Incidence rate (/100)	Hazard ratio	(95% CI)	p-value
Death or re-hospitalization									

In subgroup analyses, we will compare treatment effects in children whose caregivers report no additional antibiotic use over follow-up and separately, who report no additional azithromycin use specifically and in subsets of children defined by the following baseline characteristics: age, county of recruitment, HIV-exposure status, nutritional status, and discharge diagnosis. We will not conduct formal testing of interaction in these analyses. We will report within sub-group p-values but interpret as secondary sub-group analyses. Also in secondary analyses, we will allow more than one hospitalization and model the incidence of re-hospitalization by randomization arm using Anderson-Gill models.

We will report causes of death (and predisposing conditions in those deaths) by randomization arm (without statistical testing) as presented in Table 4.

Table 4. Causes of death by randomization arm

	Azithromycin-treated group (N=)	Placebo-treated group (N=)
Primary cause		
LRTI/Pneumonia		
Diarrhea		
Malaria		
Tuberculosis		
Other Infection		
Other non-infectious		
Predisposing conditions		
HIV		
Sickle cell disease		
Confirmed acquired condition		
Confirmed congenital condition		
None		

Statistical Analysis of Secondary Aims

In addition to the primary aim of the study to determine whether a short-course of azithromycin reduces risk of post-discharge morbidity and mortality, secondary aims include determining potential mechanisms and intermediate markers of an intervention effect, the impact of the antibiotic course on antimicrobial resistance in gut and nasopharyngeal pathogens, and correlates of post-discharge morbidity and mortality. The below tables outline these planned analyses.

Aim 2a. To evaluate possible mechanism(s) by which azithromycin may affect morbidity and mortality, by comparing reasons for re-hospitalization and prevalence of pathogens between the randomization arms.

Population	Dependent variable	Independent Variable	Covariates	Statistical model
------------	--------------------	----------------------	------------	-------------------

Reasons for re-hospitalization				
All enrolled children	Time to re-hospitalization (due to diarrhea, pneumonia, malaria, malnutrition)	Randomization arm (ITT primary and per-protocol secondary)	1) Site 2) adjusting for imbalanced baseline factors	Anderson-Gill
Enteric and nasopharyngeal pathogens				
All enrolled children	Prevalence of Shigella , Salmonella , Campylobacter , Cryptosporidium , Giardia @ 0, 3, & 6	Randomization arm (ITT primary and per-protocol secondary)	1) Site 2) adjusting for imbalanced baseline factors & baseline presence of pathogen	GEE with Poisson link & exchangeable correlation structure
	Streptococcus pneumoniae prevalence @ 0, 3, & 6	Randomization arm (ITT primary and per-protocol secondary)	1) Site 2) adjusting for imbalanced baseline factors & baseline presence of pathogen	GEE with Poisson link & exchangeable correlation structure

Aim 2b. To determine whether empiric administration of azithromycin at hospital discharge increases risk of antimicrobial resistance in commensal *E. coli* and pneumococcal isolates from treated children and their household contacts.

Population	Dependent variable	Independent Variable	Covariates	Statistical model
Resistance in enrolled children				
1. Random subset of enrolled children selected to be in the AMR sub-study 2. Children in AMR sub-study in whom E. coli was isolated	Prevalence of resistance to azithromycin and presence of extended spectrum beta-lactamase-producing E. coli . In secondary analyses, prevalence of ampicillin, chloramphenicol, ciprofloxacin, ceftriaxone, ceftazidime, gentamicin, trimethoprim-sulfamethoxazole @ 0, 3, & 6 months	Randomization arm (ITT primary and per-protocol secondary)	1) Site 2) Adjusting for imbalanced baseline factors & baseline presence of resistance 3) Adjusting for propensity score made up of factors predictive of likelihood that E. coli is isolated	GEE with Poisson link & exchangeable correlation structure. Wald tests to compare between arms and to test for time-interaction (waning in resistance from 3 to 6 months in AZM arm)
Resistance in household contacts				
1. Random subset of enrolled children selected to be in the AMR sub-study 2. Children in AMR sub-study in whom S. pneumoniae was isolated	Prevalence of resistance to azithromycin. In secondary analyses, prevalence of amoxicillin/ K clavulanate, ampicillin, chloramphenicol, clarithromycin, erythromycin, penicillin, trimethoprim-sulfamethoxazole @ 0, 3, & 6 months	Randomization arm (ITT primary and per-protocol secondary)	1) Site 2) Adjusting for imbalanced baseline factors & baseline presence of resistance 3) Adjusting for propensity score made up of factors predictive of likelihood that S. pneumoniae is isolated	GEE with Poisson link & exchangeable correlation structure. Wald tests to compare between arms and to test for time-interaction (waning in resistance from 3 to 6 months in AZM arm)

1. Randomly selected adult contacts who are participating in AMR sub-study 2. Random subset of adult AMR sub-study participants in whom E.coli was isolated	Prevalence of resistance to azithromycin and presence of extended spectrum beta-lactamase-producing E.coli . In secondary analyses, prevalence of ampicillin, chloramphenicol, ciprofloxacin, ceftriaxone, ceftazidime, gentamicin, trimethoprim-sulfamethoxazole @ 0, 3, & 6 months	Randomization arm (ITT primary and per-protocol secondary)	1) Site 2) Adjusting for imbalanced baseline factors & baseline presence of resistance 3) Adjusting for propensity score made up of factors predictive of likelihood that E.coli is isolated	GEE with Poisson link & exchangeable correlation structure. Wald tests to compare between arms and to test for time-interaction (waning in resistance from 3 to 6 months in AZM arm)
1. Randomly selected adult contacts who are participating in AMR sub-study 2. Random subset of adult AMR sub-study participants in whom S. pneumoniae	Prevalence of resistance to azithromycin. In secondary analyses, prevalence of amoxicillin/ K clavulanate, ampicillin, chloramphenicol, clarithromycin, erythromycin, penicillin, trimethoprim-sulfamethoxazole @ 0, 3, & 6 months	Randomization arm (ITT primary and per-protocol secondary)	1) Site 2) Adjusting for imbalanced baseline factors & baseline presence of resistance 3) Adjusting for propensity score made up of factors predictive of likelihood that S. pneumoniae is isolated	GEE with Poisson link & exchangeable correlation structure. Wald tests to compare between arms and to test for time-interaction (waning in resistance from 3 to 6 months in AZM arm)

Aim 3. To identify correlates and intermediate markers of post-discharge mortality and hospital-readmission among hospitalized Kenyan children.

Population	Dependent variable	Independent Variable(s)	Covariates	Statistical model
All enrolled children	Time to death or re-hospitalization	• Child nutritional status • HIV status (child & mother) • Vaccination status • Abnormal discharge • Discharge diagnosis • Length of hospital admission • Infection presence at discharge • Antibiotic resistance at discharge • Feeding practices • Socio-economic status • Caregiver education and nutritional status	Randomization arm, site	Cox proportional hazards
	Time to re-hospitalization		Randomization arm, site	Cox proportional hazards and Andersen-Gill for >1 hospitalization
	Time to death		Randomization arm, site	Cox proportional hazards

Aim 4. To determine the cost-effectiveness of post-discharge administration of a 5-day course of azithromycin in settings of varying antibiotic use, re-hospitalization rates, and mortality rates.

Costs analysis: We will assess the costs of all supplies, services and equipment necessary to implement the intervention (direct medical costs). The perspective will be that of the healthcare provider, i.e. Kenya's Ministry of Health. Using WHO guidelines and its ingredients approach, we will quantify the resources and associated unit costs required to deliver a 5-day course of azithromycin, organized in Version 5.0

standard expenditure categories: personnel (salaries), supplies including drugs, equipment, services, space and overhead. We will also measure the costs of severe child hospitalizations, the costs for the different types of personnel employed (e.g. nurses/doctors) and the time demanded from them for conducting the intervention. When data are missing, they will be complemented by data extracted from the literature and other available sources. Full incremental costs will be derived, with estimation of the potential healthcare cost-offset realized in avoiding severe hospitalizations. Costs will be measured in local currency (Kenyan Shilling) and converted into US\$. Our main metric will be cost per child treated.

Cost-effectiveness analysis (CEA): we will develop a CEA mathematical model, and estimate incremental costs and cost-effectiveness for implementation of the intervention. The model will include two components: costs (described immediately above) and health benefits. The study will provide clinical outcomes (mortality/morbidity) over a 6-month follow-up period. Subsequently, deaths averted, life-years saved and disability-adjusted life years (DALYs) averted by the intervention will be estimated. We will estimate: a) incremental costs and b) incremental cost-effectiveness of the intervention vs. status quo. *Incremental costs* are the net sum of the costs to implement the intervention compared with status quo, and the costs averted due to the decrease in severe child hospitalizations. *Incremental cost-effectiveness* ratios (ICERs) will be estimated as cost per death averted, cost per life-year saved, and cost per DALY averted. We will use recent estimates of disability weights for estimation of DALYs. Short-term (over study follow-up i.e. 6 months) and longer-term time horizons (extrapolated to 1, 5, and 10 years) will be used. DALYs and costs will be discounted at 3% per year, consistent with CEA guidelines (undiscounted results will also be presented). Sources of uncertainty in the results will be explored in univariate and probabilistic sensitivity analysis. Finally, we will compare our findings to CEA estimates for other health interventions in sub-Saharan Africa.

Missing Data

